8.12. Management of treatment dose adaptations due to toxicities

For patients who do not tolerate the protocol-specified dosing schedule, dose interruptions and/or reductions are either recommended or mandated in order to allow patients to continue the study treatments.

Dose modifications recommendations for S64315 are summarised in [Table \(8.12\) 1](#).

A patient must discontinue treatment with S64315 if, after treatment is resumed at a lower dose, the toxicity recurs with the same or worse severity, unless in the opinion of the investigator it is in the patient's best interest to continue S64315, and upon documented agreement with the Sponsor.

For each patient, once a dose reduction has occurred, the dose may not be re-escalated during the subsequent cycles unless in the opinion of the investigator it is in the patient's best interest to continue S64315, and upon documented agreement with the Sponsor.

When a patient meets the criteria for S64315 discontinuation described in the table, he/she must discontinue both IMPs.

Dose modifications for azacitidine must be done according to azacitidine E.U. SmPC (see [Table \(8.12\) 2](#)).

These dose changes must be recorded in the eCRF.

Table (8.12) 1 - Criteria for interruption and re-initiation of S64315

Recommended dose modifications for S64315	
Worst toxicity CTCAE Grade^a (unless otherwise specified)	During a cycle of therapy
Investigations (Renal)	
Serum creatinine	
Grade 2 (> 1.5 – 3 x ULN or > 1.5 – 3 x baseline)	Omit dose until resolved to Grade ≤ 1 or baseline, then: - If resolved in ≤ 14 days, then maintain dose level - If resolved in > 14 days, then ↓ 1 dose level
Grade 3 (> 3 – 6 x ULN or > 3 x baseline)	Omit dose until resolved to Grade ≤ 1 or baseline, then ↓ 1 dose level
Grade 4 (> 6 x ULN)	Discontinue patient from test drug treatment
Note: If intercurrent illness, e.g. dehydration due to diarrhoea or febrile infections, leads to prerenal insufficiency, this should not be considered drug related and the criterion for dose modification not fulfilled	
Investigations (Hepatic)	
Isolated Total Bilirubin elevation^b	
Grade 2 (> 1.5 - 3.0 x ULN if baseline was normal, >1.5 - 3.0 x baseline if baseline was abnormal)*	Omit dose until resolved to Grade ≤ 1, then: - If resolved in ≤ 14 days, maintain dose - If resolved in > 14 days, ↓ 1 dose level

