> 2.0 - 5.0 x ULN and asymptomatic	Omit dose until resolved to Grade ≤ 1 or baseline then: 
 - If resolved in ≤ 14 days, maintain dose level - If resolved in > 14 days, ↓ 1 dose level
Grade 3 (> 2.0 - 5.0 x ULN with signs or symptoms or >5.0 x ULN and asymptomatic)	Discontinue patient from test drug treatment
Grade 4 (> 5.0 x ULN and with signs or symptoms)	Discontinue patient from test drug treatment

Note: A CT scan to assess the pancreas, liver, and gallbladder must be performed within 1 week of the first occurrence of any Grade ≥ 3 amylase and/or lipase, or as clinically indicated

Investigation (Metabolic)**Creatine (phospho)kinase elevation**

Grade 3	Omit dose until resolved to Grade ≤ 2, then: 
 - If resolved in ≤ 14 days, maintain dose level - If resolved in > 14 days, ↓ 1 dose level
Grade 4	Omit dose until resolved to Grade ≤ 2, then: 
 - If resolved in ≤ 14 days, then ↓ 1 dose level - If resolved in > 14 days, then discontinue patient from test drug treatment

Gastro intestinal	
Pancreatitis	
Grade \geq 3	Discontinue patient from test drug treatment
Diarrhoea	
Grade 1 and 2 ^g	Maintain dose level, treat the patient per institutional diarrhoea management protocol
Grade 3	Omit dose until resolved to Grade \leq 1, treat the patient per institutional diarrhoea management protocol, then: 
 - If resolved in \leq 5 days, maintain dose level - If resolved in $>$ 5 days despite the use of optimal anti-diarrhoea therapy, \downarrow 1 dose level
Grade 4	Discontinue patient from test drug treatment.
Grade \geq 3 Vomiting	Maintain dose level, if not resolved to Grade \leq 2 within 48h after start of optimal anti-emetic therapy, then omit dose until resolved to Grade \leq 2, and then \downarrow 1 dose level
Metabolism and nutrition disorders	
Electrolyte abnormalities (if clinically significant)	
Grade 3	Omit dose until resolved to Grade \leq 1, then: 
 - If resolved in \leq 7 days, maintain dose level - If resolved in $>$ 7 days, \downarrow 1 dose level
Grade 4	Discontinue patient from test drug treatment
Skin and subcutaneous tissue disorders	
Rash /photosensitivity	
Grade 1	Maintain dose level Consider initiating appropriate skin toxicity therapy (e.g. antihistamines and topical corticosteroids) as per local institutional guidelines Consider skin biopsy for evaluation

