4.2.3.4. Clinical laboratory evaluation**Values**

Only reliable values are considered for analyses. Unreliable values are flagged into the database.

WBC differentiation, including values of neutrophils, basophils, eosinophils, monocytes, lymphocytes and blasts, will be ignored if blast value is missing/not done or the differentiation is automated, as considered not reliable.

In case of **multiple samples**:

- Each post-baseline value (test, re-test, planned, unplanned) measured under treatment is taken into account for analyses.

Units

All parameters will be analysed in international units (IU).

Abnormal values

Abnormal values are described according to:

- Reference laboratory ranges for the non-gradable parameters.
- NCI-CTCAE version 5.0 grade for gradable parameters.

Laboratory reference limits and NCI-CTCAE version 5.0 grades are reported in the database.

For the parameters which are gradable according to CTCAE v5.0, the grades will be derived using the local laboratory reference limits in analysis datasets.

Table (4.2) 4 - Definition of CTCAE grade - Version 5.0 - Gradable parameters

Parameter	Grade 1	Grade 2	Grade 3	Grade 4
Sodium (mmol/l) – Hypernatremia]ULN;150]]150;155]]155;160]	>160
Sodium (mmol/l) - Hyponatremia	[130;LLN[-	[120;130[< 120
Potassium (mmol/l) – Hyperkalemia]ULN;5.5]]5.5;6]]6;7]	> 7
Potassium (mmol/l) – Hypokalemia		[3.0;LLN[[2.5;3.0[< 2.5
Amylase (IU/L) - High	>ULN – 1.5 x ULN	>1.5 x ULN – 2 x ULN	>2 x ULN – 5 x ULN	> 5 x ULN
Triacylglycerol Lipase (IU/L) - High	>ULN – 1.5 x ULN	>1.5 x ULN – 2 x ULN	>2 x ULN – 5 x ULN	> 5 x ULN
Ionized calcium (mmol/l) - High]ULN;1.5]]1.5;1.6]]1.6;1.8]	> 1.8
Ionized calcium (mmol/l) - Low	[1.0;LLN[[0.9;1.0[[0.8;0.9[< 0.8
Magnesium (mmol/l) - Hypermagnesemia]ULN;1.23]	-]1.23;3.30]	> 3.30
Magnesium (mmol/l) - Hypomagnesemia	[0.5;LLN[[0.4;0.5[[0.3;0.4[< 0.3
Albumin (g/l) - Low	[30; LLN[[20; 30[< 20	-
Glucose (mmol/l) - Hypoglycemia	[3.0;LLN[[2.2;3.0[[1.7;2.2[< 1.7
Total cholesterol (mmol/l) - High]ULN;7.75]]7.75;10.34]]10.34;12.92]	> 12.92
Triglycerides (mmol/l) - High	[1.71;3.42]]3.42;5.7]]5.7;11.4]	> 11.4
Serum creatinine increased (umol/L)	>ULN – 1.5 x ULN	>1.5 x baseline – 3.0 x baseline (if baseline available) OR >1.5 x ULN – 3.0 x ULN	>3.0 x baseline (if baseline available) OR >3.0 x ULN – 6.0 x ULN	>6.0 x ULN

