AST increased (IU/L)	>ULN – 3.0 x ULN if baseline is normal [\leq ULN]; 1.5 x baseline – 3.0 x baseline if baseline is abnormal [> ULN]	>3.0 x ULN – 5.0 x ULN if baseline is normal [\leq ULN]; >3.0 x baseline – 5.0 x baseline if baseline is abnormal [> ULN]	>5.0 x ULN – 20.0 x ULN if baseline is normal [\leq ULN]; >5.0 x baseline – 20.0 x baseline if baseline is abnormal [> ULN]	>20.0 x ULN if baseline is normal [\leq ULN]; >20.0 x baseline if baseline is abnormal [> ULN]
GGT increased (IU/L)	>ULN – 2.5 x ULN if baseline is normal [\leq ULN]; 2.0 x baseline – 2.5 x baseline if baseline is abnormal [> ULN]	>2.5 x ULN – 5.0 x ULN if baseline is normal [\leq ULN]; >2.5 x baseline – 5.0 x baseline if baseline is abnormal [> ULN]	>5.0 x ULN – 20.0 x ULN if baseline is normal [\leq ULN]; >5.0 x baseline – 20.0 x baseline if baseline is abnormal [> ULN]	>20.0 x ULN if baseline is normal [\leq ULN]; >20.0 x baseline if baseline is abnormal [> ULN]

Any grade corresponds to a laboratory value with NCI-CTCAE version 5.0 grade 0, 1, 2, 3 or 4.

A grade 0 corresponds to a laboratory value within limit or reference range.

The LOWEST value for a patient is defined as the lowest absolute laboratory value during the treatment period.

A lowest value for a cycle is defined as the lowest laboratory value in that cycle.

The time to lowest value is defined from the date of the first IMP intake to the sampling date of the lowest value.

The time to lowest value in a cycle is defined from the first date of IMP intake in that cycle to the sampling date of the lowest value.

The HIGHEST value for a patient is defined as the highest laboratory value during the treatment period.

A highest value for a cycle is defined as the highest laboratory value in that cycle.

The time to highest value is defined from the date of the first IMP intake to the sampling date of the highest value.

Urinary results

The category positive includes results '+', '++', '+++', and '++++'.

The category negative corresponds to 'Absent' class.

Creatinine clearance

Creatinine clearance will be approximated by MDRD_GFR. This will be calculate as:

$\text{MDRD_GFR (mL/min/1.73m}^2\text{)} = 175 \times (\text{serum creatinine in mg/dL})^{-1.154} \times \text{age}^{-0.203} \times 0.742$ (if female) $\times 1.212$ (if black race).

Serum creatinine conversion:

$\text{Serum creatinine (mg/mL)} = \text{Serum creatinine (}\mu\text{mol/L)}/88.4$.

MDRD_GFR will be categorised in 4 categories:

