- Normal renal function (MDRD_GFR >90 mL/min/1.73m²).
- Mild renal impairment (MDRD_GFR 60-90 mL/min/1.73m²).
- Moderate renal impairment (MDRD_GFR 30-59 mL/min/1.73m²).
- Severe (MDRD_GFR <30mL/mn/1.73m²).

Worst value

Worst value will be analysed as follow:

- For the urinalysis parameters, the worst class will correspond to 'Positive' class, then 'Trace' and finally 'Negative' will be considered as normal class.
- For creatinine clearance, the worst class will correspond to "severe" category, then "moderate", then "mild" and finally "normal".
- Baseline and post baseline worst grade for High and Low:
 - Low: If the result is below lower normal range limit, low =grade (for gradable parameter) or result (for non-gradable parameter), Else low=0.
 - High: If the result is above upper normal range limit, high =grade (for gradable parameter) or result (for non-gradable parameter), Else high =0.

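### SAP grading sets in-range creatinine rises above 1.5 x baseline to Grade 0, against its own table, and above 2 x ULN grades amylase and lipase without the protocol's symptom condition

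*SAP*

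**What the plan says.** **Creatinine.** SAP Table (4.2) 4 gives Grade 2 as ">1.5 x baseline – 3.0 x baseline (if baseline available) OR >1.5 x ULN – 3.0 x ULN" and Grade 3 as ">3.0 x baseline (if baseline available) OR >3.0 x ULN – 6.0 x ULN". Protocol Table (8.12) 1 uses the same two-way criterion: "Grade 2 (> 1.5 – 3 x ULN or > 1.5 – 3 x baseline", with Grade 3 likewise reached above 3 times baseline. None of these entries requires the value to be above ULN. Two later statements in the same SAP section do. One is the definition of Grade 0: "A grade 0 corresponds to a laboratory value within limit or reference range". The other is the worst-grade rule: "High: If the result is above upper normal range limit, high =grade (for gradable parameter) or result (for non-gradable parameter), Else high =0".

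**Amylase and lipase.** In SAP Table (4.2) 4 the row "Triacylglycerol Lipase (IU/L) - High" and the matching amylase row assign Grade 3 to values above 2 and up to 5 x ULN, and Grade 4 above 5 x ULN. Neither has a symptom condition. Protocol Table (8.12) 1 has a row "> 2.0 - 5.0 x ULN and asymptomatic" with no grade printed on it, followed by "Grade 3 (> 2.0 - 5.0 x ULN with signs or symptoms or >5.0 x ULN and asymptomatic", and keeps Grade 4 for values above 5 x ULN with signs or symptoms. Both documents say they use CTCAE v5.0.

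**Where the grades go.** SAP section 3.4.4 plans tables of worst on-treatment grade against baseline grade, and protocol section 10.4.4.2 plans the corresponding shift tables. SAP Table (3.4.4) 1 lists creatinine, amylase and lipase in the high direction only. Section 4.2.3.4 derives the grades in the analysis datasets from local laboratory limits.

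**The concern.** For creatinine, one SAP section gives two answers for the same sample, and a programmer cannot satisfy both. If the later rule is followed, a patient whose creatinine doubles inside the reference range is tabulated as having no renal laboratory change.

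For amylase and lipase, the SAP and the protocol give different grades to the same asymptomatic value under the same stated version of CTCAE.

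Laboratory tests are endpoints of the primary objective (SAP section 1.2). Efficacy is not analysed in the abbreviated report (SAP sections 1 and 3.3), so the safety tables carry the report. Because grades are derived from the numbers, an investigator's own grading would not correct the laboratory tables.

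**Working it through.** There is no sample size, power or error rate to reproduce. The check applies the written rules to the same values.

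**1. When the creatinine conflict can occur.** Let b be baseline and v the on-treatment value. The table gives at least Grade 2 if v > 1.5b. The High rule gives 0 if v ≤ ULN. Both hold when 1.5b < v ≤ ULN, which is possible only if b < ULN/1.5 = 0.67 x ULN. For a table Grade 3 set to 0, the condition is 3b < v ≤ ULN, so b < ULN/3.

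The documents give no ULN for creatinine. Over an assumed range:

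| Assumed ULN (µmol/L) | Grade 2 set to 0 possible if b below | Grade 3 set to 0 possible if b below |
|---|---|---|
| 80 | 53.3 | 26.7 |
| 90 | 60.0 | 30.0 |
| 104 | 69.3 | 34.7 |
| 110 | 73.3 | 36.7 |
| 120 | 80.0 | 40.0 |

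**2. Creatinine examples (assumed ULN 104 µmol/L).**
- b = 50, v = 100: ratio 2.0, v ≤ ULN. Table Grade 2, High rule 0.
- b = 30, v = 96: ratio 3.2, v ≤ ULN. Table Grade 3, High rule 0.

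**3. Are such baselines eligible?** Inclusion criterion 16 requires MDRD clearance above 60, which favours low creatinine. Take a woman aged 68 (the 1.212 race factor not applied) and the SAP formula 175 x Scr^-1.154 x age^-0.203 x 0.742:
- Scr 0.60 mg/dL gives 99.4.
- Scr 0.95 mg/dL gives 58.5; the ratio is 0.95/0.60 = 1.58.

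With an assumed ULN of 0.95 to 1.1 mg/dL, the table gives Grade 2 and the High rule gives 0. With a ULN of 80 µmol/L (80/88.4 = 0.905 mg/dL), 0.95 is above ULN and both give Grade 2. The example therefore depends on the local limit; the condition in step 1 does not.

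**4. Is creatinine the only baseline-relative row affected?** ALT, AST, ALP, GGT and bilirubin use multiples of baseline only when baseline is already above ULN, so the High rule changes nothing there. The raised-haemoglobin row states the above-ULN condition itself. Creatinine is the only row using baseline that lacks the condition and is overridden by the rule.

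**5. Amylase and lipase.**

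| Value (x ULN) | Symptoms | SAP grade | Protocol grade |
|---|---|---|---|
| 1.2 | no | 1 | 1 |
| 1.8 | no | 2 | not printed; 2 by position |
| 3 | no | 3 | not printed; 2 by position |
| 3 | yes | 3 | 3 |
| 6 | no | 4 | 3 |
| 6 | yes | 4 | 4 |

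The two documents differ only for asymptomatic values above 2 x ULN, by one grade each time. In the band above 2 and up to 5 x ULN, that one grade rests on the inferred Grade 2.

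**The case against.** The strongest reply is that little depends on this column of grades, and much of it stands.

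- **Dose holds for creatinine.** A reader might infer that renal events for which drug was held would vanish from the report. The documents do not support that. Protocol section 8.2 requires a laboratory abnormality that delays dosing to be reported as an adverse event, unless it supports a diagnosis already reported as one. SAP section 3.4.2 tabulates emergent events by worst grade and action taken. SAP section 3.2.5.1 reports interruptions and their reasons. Creatinine clearance is also tabulated by MDRD class, so the patient in step 3 would show as moving from normal to moderate.
- **DLTs.** A reader might infer that DLT counts change, or that the laboratory and DLT tables would contradict each other. SAP section 4.2.3.1 takes DLTs from the investigator's page without re-deriving them, so counts do not change. The DLT table also requires relatedness and covers events before the end of cycle 1 in the DLT-evaluable set. The laboratory tables cover the whole treatment period in the safety set with no causality filter. A Grade 3 laboratory value without a DLT is therefore no contradiction in itself. Asymptomatic values above 5 x ULN are at least Grade 3 in both schemes, so only the asymptomatic band above 2 and up to 5 x ULN crosses the Grade 3 line.
- **Scale.** These are descriptive tables in an abbreviated report of a stopped phase I study.

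This limits the consequence. It does not remove the conflict: the laboratory grade tables cannot be programmed consistently with both the SAP's table and its High rule.

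**Conclusion.** The point holds in a limited form. For creatinine, the SAP contradicts its own grade table and the protocol: the Grade 0 definition and the High rule erase any in-range rise above 1.5 times baseline, including rises above 3 times baseline that the table calls Grade 3. For amylase and lipase, the SAP table conflicts with the protocol, not with itself, and only for asymptomatic values above 2 x ULN. It would be wrong to say that all asymptomatic rises are over-graded, because up to 2 x ULN there is no conflict.

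The size is up to two or three grades for an affected creatinine value and one grade for an affected amylase or lipase value, in the worst-grade and shift tables only. How many patients are affected cannot be derived from the documents. The creatinine windows rest on assumed ULNs of 80 to 120 µmol/L. The Grade 2 reading of the protocol's unlabelled amylase and lipase row is inferred from its position. The conflict should be corrected because the outputs belong to a primary-objective endpoint and the repair is cheap.

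**What to change.** 1. **Creatinine.** State in SAP section 4.2.3.4 that Table (4.2) 4 determines the creatinine grade. Add a creatinine exception in two places: the sentence defining Grade 0 and the High rule under worst value. Changing only one leaves the contradiction in place.
2. **Amylase and lipase.** Reconcile the bands in SAP Table (4.2) 4 with protocol Table (8.12) 1. Alternatively, since neither document provides for recording symptoms with the samples, drop the grade and tabulate by multiple of ULN, using cut-points already in both documents: up to 1, above 1 to 1.5, above 1.5 to 2, above 2 to 5, above 5. Linking samples to pancreatic adverse events by date would need a derivation that neither document defines; the ULN classes avoid it.

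The cost is a few lines of SAP text, matching changes to the grade derivation and table shells, and no new data collection. Nothing here asks for a change to the protocol's dose-modification rules.

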4.2.3.5. Vital signs, clinical examination and other observations related to safety

4.2.3.5.1. Vital signs and clinical examination

Worst value

For ECOG, SBP, DBP and HR, the worst (highest) value will be derived.

For Weight, SBP, DBP and HR, the worst (lowest) value will be derived.

ECOG performance status

GRADE	STATUS
ECOG - ZUBROD / WHO	
0	Normal unrestricted activity
1	Arduous physical activity restricted, but patient able to walk unaided and perform light work
2	Able to walk unaided and independent but unable to work more than half-time
3	Much less independent. Spends more than half his / her time in bed or seated.
4	Incapable of looking after him / herself. Completely confined to bed or to a chair

4.2.3.5.2. Electrocardiogram**Multiple samples**

For the analysis of QT criteria per measurement time, only values at each scheduled post-baseline visits are analysed. All data obtained from triplicate ECGs are taken into account in the analysis. For these schedule ECGs, for each measurement time, the mean of available values is calculated and taken into account in the analyses.

The measurement times of QT criteria will be those fulfilled in the database and transferred by Banook Group.

QT corrected

QTcF: QT corrected using Fredericia's formula is calculated as follows:

$$QTcF (msec) = \left(\frac{QT(msec)}{(60/(HR(bpm)))^{1/3}} \right)$$

For all other analyses, all analysable values are taken into account, whether at planned visit or not, initial sample or additional sample.

ECG abnormality:

ECG abnormality corresponds to ECG for which the conclusion is ABNORMAL, NOT CLINICALLY SIGNIFICANT or ABNORMAL, CLINICALLY SIGNIFICANT.

Clinically significant ECG abnormality:

Clinically significant ECG abnormality corresponds to ECG for which the conclusion is ABNORMAL, CLINICALLY SIGNIFICANT.

Emergent ECG abnormality / Emergent clinically significant ECG abnormality:

Occurrence of emergent ECG abnormality / emergent clinically significant ECG abnormality after the first study treatment administration date (included) are defined as follows:

S 64315

CL1-64315-004 – Statistical Analysis Plan – Final V1.0

Triplicates Baseline		Record on treatment	Emergence Abnormality ECG	Emergence Significant Abnormality ECG
All ECG within normal limit	and	Abnormality no significant	Yes	No
All ECG within normal limit	and	Abnormality significant	Yes	Yes
At least one line “Abnormality no significant “ and no line “Abnormality significant”	and	Abnormality significant	No	Yes
No baseline	or	No post baseline	Missing	Missing
If triplicate baseline is not missing and records on treatment are not missing and the combination is not covered by the previous cases.			No	No

Maximum absolute prolongation during treatment period = max (Absolute prolongation during treatment period).

Maximum change from baseline = Maximum absolute prolongation - Absolute prolongation at baseline.

4.2.3.5.3. LVEF

For this parameter, the worst value will correspond to the *lowest* measure.

Analysis by grade according NCI-CTCAE version 5.0:

Grade 0: other cases.

Grade 2: LVEF [40 – 50%] or Change [-20; -10%].

Grade 3: LVEF [20 – 40%] or Change < -20%.

Grade 4: LVEF < 20%.

4.2.4. Biomarkers

N/A.

